#### Risks

**Physical Risks:** Patients and caregivers will receive transitional care in the SNF and in the patient's home. Transitional care activities involve verbal assessments, conversation, education, and planning. There is a possibility that participants could be fatigued from participation in the data collection activities. For example, while participating in a care-planning meeting, a patient might feel fatigued or need to take a break. Protection: If any participant has a physical injury, the study team will help them seek immediate medical attention. If a SNF patient or caregiver expresses fatigue during data collection, the data collection session will be terminated immediately, and a follow-up appointment scheduled.

**Psychological Risks:** Emotional distress related to learning more about medical and functional challenges and plans for care at home is a potential psychological risk. Staff in the SNF and in the home after discharge will engage patients and caregivers in conversations to plan strategies for managing illness at home. Also, during enrollment and data collection activities, staff will assess the patients' quality of life, functional mobility, falls at home, days at home without acute care use and caregivers' burden and distress related to the caregiving role. These study-related activities may also involve a chance for emotional distress. Protection: The study team will refer distressed patients and caregivers to their attending or primary care physicians for support with emotional distress.

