- Dementia Quality of Life-Proxy measure (DEMQOL-Proxy). When the patient is unable to rate their quality of life, the quality of life will be rated by their caregiver, using the Dementia Quality of Life-Proxy measure.(33) The score range is 31-124 with higher scores indicating better quality of life.
- Self-Reported Days of ED or Hospital Use 30 Days After Skilled Nursing Facility Discharge. Patient's days of acute care use will be measured using the self-reported number of combined number of days the patients pends in the Emergency Department (ED) or hospital in 30 days after SNF discharge.(19)
- Zarit Caregiver Burden Scale. Caregiver burden will be measured using the Zarit Caregiver Burden Scale, which includes 12 items on a five-point scale, measuring caregiver perceptions that "caregiving has an adverse effect on their emotional, social, financial, physical and spiritual functioning."(34) Scores range 0-48; higher scores are associated with depression and social isolation.
- Distress Thermometer. Caregiver distress will be measured using the Distress Thermometer, which includes 1 item on an 11-point scale, measuring negative affect (e.g., sadness and fear) related to caregiving for a severely ill person. Score ranges 0-10, with scores >4 associated with poor coping and depression.(35)

a. Safety Evaluations

- Study progress and safety will be reviewed monthly (and more frequently if needed). Progress reports will include patient and caregiver recruitment, retention/attrition, and adverse events. In addition, safety evaluation will include (1) whether adverse event rates are consistent with pre-study assumptions; (2) reason for dropouts from the study; (3) whether all participants met entry criteria; (4) whether continuation of the study is justified on the basis that additional data are needed to accomplish the stated aims of the study; and (5) conditions whereby the study might be terminated prematurely.
- An adverse event (AE) is any untoward medical occurrence in a subject temporally associated with participation in the clinical study or with use of the experimental agent being studied. An adverse finding can include a sign, symptom, abnormal assessment or any combination of these. A Serious Adverse Event (SAE) is any adverse event that results in one or more of the following outcomes:
  - Death
  - A life-threatening event
  - Inpatient hospitalization
  - A persistent or significant disability/incapacity

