  - Important medical event based upon appropriate medical judgment

Potential sources of information for identification of AEs include (but may not be limited to) nursing home staff reports of events while the patient is in the nursing home, and patient or caregiver reports of events while the patient is in the nursing home or at home. For example, the proposed study team will be in contact with the patient and caregiver over 30 days after the patient discharges from the nursing home to home. We will be calling the patient and caregiver at 7, 21 and 30 days. Any event that is discovered will be immediately relayed to the PI, or if he is away, another member of the research team so that we can execute safety plans and reporting plans described here.

AEs will be labeled according to severity, which is based on their impact on the patient. An AE will be termed 'mild' if it does not have an impact on the patient, 'moderate' if it causes the patient some minor inconvenience

and ‘severe’ if it causes a substantial disruption to the patient’s well-being. AEs will be categorized according to the likelihood that they are related to the study intervention. Specifically, they will be labeled either definitely, probably, possibly or unrelated to the study intervention. If any IRB actions occur, the PI will email a report within 24 hours for the Independent Monitor, the second Independent monitor, and the Program Officer in the NINR in accordance with requirements.

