Any serious adverse events or deaths that occur during the study will be reported by telephone immediately to the Human Participants Research Review Committee Chairperson. An incident report will be sent by electronic mail by the Executive Committee members and the project manager. The PI will follow-up immediately with patient or caregiver to investigate, and prepare a report for all members of the Human Participants Committee, and comply with all regulations regarding the reporting of serious adverse events. The event will be evaluated for relatedness to the study intervention. The PI or a Co-Investigator in his absence will be responsible for complying with all regulations concerning the reporting of a serious adverse event and will prepare a full report for NIH if the event is related to study intervention. The PI will meet with the Co-Investigators and project manager and make a subject or study termination decision as the situation warrants. Process notes will be kept concerning any termination decisions.

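### Adverse event causality is judged only against the study intervention, so an event caused solely by a research interview can only be labelled unrelated

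*Combined protocol and SAP*

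**What the plan says.** Section 7, Safety Evaluations, defines an adverse event as "any untoward medical occurrence in a subject temporally associated with participation in the clinical study", or with use of the experimental agent. It then grades each event in two ways. One is severity: "AEs will be labeled according to severity, which is based on their impact on the patient". The other is cause: "AEs will be categorized according to the likelihood that they are related to the study intervention". The permitted answers follow at once: "Specifically, they will be labeled either definitely, probably, possibly or unrelated to the study intervention".

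Section 10, Safety Management, also evaluates serious events for relatedness to the study intervention. It says the principal investigator (or a co-investigator in his absence) "will prepare a full report for NIH if the event is related to study intervention". The same section promises standards for withdrawing subjects because of related adverse events, without saying what they must be related to.

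Section 3, Risks, names data collection as a source of harm. On physical risk: "There is a possibility that participants could be fatigued from participation in the data collection activities". On psychological risk, after listing the enrollment and data collection assessments: "These study-related activities may also involve a chance for emotional distress".

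The Safety Analysis in Section 8 describes adverse events with descriptive statistics and does not mention source.

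**The concern.** The net that catches adverse events is wider than the scale that explains them. Events can enter through study participation or through the intervention, but only the second route has a causal question attached. The protocol expects its own interviews to tire or upset some people. The sample is cognitively impaired patients and their caregivers, and the interviews ask about burden, distress and quality of life.

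Two things are at stake. First, the relatedness label decides whether a serious event gets a full NIH report. Second, the pilot is meant to inform a later trial that may reuse the same interviews. A safety table built on these labels would show interview-caused distress as unrelated, so it would say nothing about how well the interviews were tolerated.

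**Working it through.** The plan gives no figure to reproduce. The check is whether the rules, read together, leave any label other than unrelated for an event caused solely by a research interview.

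1. **Is such an event an adverse event?** Yes, if it is a medical occurrence. Section 7 covers events "temporally associated with participation in the clinical study or with use of the experimental agent being studied". The two routes are joined by *or*, so participation alone is enough.

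2. **Are the interviews part of the intervention?** No. Section 6b and Section 9 (with Tables 4 and 5) describe Connect-Home Plus as transitional care in the SNF, a home care nurse visit and calls from the dementia caregiving specialist. The baseline, 7-, 21- and 30-day research interviews are not listed. Section 6e draws the same line: it describes subjects who stop after the recruitment questionnaires but before receiving the intervention. An event in that interval cannot have been caused by the intervention.

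3. **Does the protocol expect such events?** Yes, for fatigue and emotional distress (Section 3, Risks).

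4. **Which label fits?** Section 7 offers four, all relative to the study intervention. If the intervention played no part, *definitely*, *probably* and *possibly* are all wrong. Only *unrelated* remains. Severity is also graded, but it records impact and not cause.

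5. **What follows from the label?** For a serious event, Section 10 makes the full NIH report conditional on relatedness to the intervention. An event labelled unrelated does not meet that condition.

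6. **Does any other section supply the missing attribution?** No. The Safety Analysis in Section 8 does not separate sources. Section 10 has the safety committee watch the risk of the study as a whole, but defines no attribution for doing so.

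**Number of interviews.** The inputs are 20 dyads (Section 5c), 2 participants per dyad, and 4 research contacts each: baseline, day 7, day 21 and day 30 (schedules in Section 6c).

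- Patients: 20 × 4 = 80
- Caregivers: 20 × 4 = 80
- Total: 80 + 80 = 160

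This is the planned maximum. Sections 5a and 6 let outcome data come from the caregiver alone when the patient cannot take part, and Section 7 lets baseline patient data come from the caregiver or representative. The figure counts opportunities for an event, not events.

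**The case against.** The strongest reply is that very little goes missing. An interview-caused event is still an adverse event, any event discovered is relayed to the principal investigator at once, and the Safety Analysis is not restricted to related events. All serious events and deaths are telephoned in whatever their cause and written up for the review committee. Interview fatigue and distress already have protections (ending the session, referral). Few interview effects would be serious enough to reach the NIH rule. All of this stands, and it limits the consequence. None of it supplies an attribution to research procedures.

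The reply also disposes of four stronger readings that a reader might infer.

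- **That the withdrawal standards also exclude research harm.** Section 10 does not say what *related* refers to there, and the standards are still to be written. The text is silent, not exclusive.
- **That any harm arising in an interview is unrelated by rule.** The caregiver schedule places specialist calls in the same day-7 and day-21 windows as the interviews, and the Risks text also ties fatigue and distress to care-planning activities. When the cause is mixed, *possibly* is available. The rule forces *unrelated* only when the interview is the sole cause.
- **That embarrassment and loss of confidentiality must be labelled unrelated too.** Section 3 links both to enrollment and data collection, but the definition requires a medical occurrence. They may never reach the relatedness scale, so the point rests on fatigue and distress alone.
- **That 160 measures the problem.** It is a ceiling on interviews, and no rate of interview-related events is given.

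**Conclusion.** The point holds in a limited form. As written, an adverse event caused solely by a research interview can only be labelled unrelated, and a serious one would fall outside the full NIH report. The loss is source attribution plus that one report trigger. Capture of the event, its place in the overall adverse event count and the telephone report of serious events are all intact. A reader might infer that study-caused harm disappears from the safety summary. The documents do not support that: the events are counted, but without a correct source.

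No primary or secondary outcome is affected, and the number of events concerned cannot be estimated from the documents. The conclusion assumes that *study intervention* means Connect-Home Plus, as the protocol uses the term, and that the fatigue or distress is marked enough to count as a medical occurrence. The change is still worth making, because the protocol itself foresees the harm and the correction is almost free.

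**What to change.** - **Section 7, Safety Evaluations, and Section 10, serious events:** make two relatedness judgements on the same four-level scale, one for the study intervention and one for the research procedures (recruitment, interviews, record handling).
- **Section 10, NIH report:** let relatedness to either source trigger the full report.
- **Section 10, standards for related adverse events:** state that *related* covers both sources. The content of those standards remains for the study team and the safety committee.
- **Section 8, Safety Analysis:** tabulate adverse events by relatedness to each source separately.

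The cost is protocol wording and one extra field on the adverse event form. The count of related events may rise slightly. Sample size, visit schedule and outcomes do not change.

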## **8. STATISTICAL CONSIDERATIONS**

The study will provide descriptive data about the feasibility and acceptability of the Connect-Home Plus Intervention, and to provide a description of patient and caregiver outcomes in the small sample of participants in the feasibility and acceptability study. Therefore, a small sample 20 patients and their caregivers will be used to achieve these goals.

### **Primary Endpoint**

The sample of 20 patients and their 20 caregivers is sufficient to determine feasibility (i.e., the extent that staff will be able to deliver components of the Connect-Home Plus as intended) and the acceptability of Connect-Home Plus (i.e., the perceptions of the patients and caregivers that the intervention is easy to use, helpful, and provides skills for care of the patient at home).

### **Secondary Endpoint**

The sample of 20 patients and their 20 caregivers is sufficient to describe preparedness for care after discharge (patient and caregiver); patient quality of life, functional mobility and acute care use; and caregiver burden and distress.

### **Statistical Methods**

- Baseline data. Descriptive statistics will be used to analyze data collected in baseline surveys and chart reviews and describe patient clinical and non-clinical characteristics. Descriptive statistics will also be used to analyze baseline data collected from caregivers and describe nonclinical characteristics of caregivers.
- Efficacy Analysis. The study will not include an analysis of efficacy; rather, descriptive statistics will be used to describe the feasibility and acceptability of the intervention and to describe patient and caregiver outcomes in 30 days after SNF discharge. The primary outcome evaluation will use descriptive statistics to describe feasibility of providing the 8 intervention components identified in the feasibility chart review guide. The primary outcome evaluation will also use descriptive statistics to describe the acceptability of Connect-Home Plus. In addition, the secondary outcome evaluation will use descriptive statistics to describe preparedness for care after discharge (patient and caregiver); patient quality of life, functional mobility and acute care use; and caregiver burden and distress.
- Safety Analysis. Descriptive statistics will be used to describe patient and caregiver recruitment, retention/attrition, and adverse events.

### **Sample Size and Power**

- 20 persons with ADRD and 20 caregivers in 2 SNFs over 12 months to determine the feasibility and acceptability of the adapted intervention.

### **Interim Analysis**

- None

## **9. STUDY INTERVENTION**

Connect-Home Plus will introduce new organizational structure to support staff delivery of transitional care processes.(19) Consistent with Donabedian, we anticipate that these changes in structure and care processes will be associated with improved patient and caregiver outcomes. New elements of organizational structure include an EHR template, the Connect-Home Toolkit, and Staff Training protocols; we developed, refined and tested these, finding them to be feasible, acceptable, and associated with improved patient and caregiver experiences of care.(1) See Table 4.

**Table 4. Connect-Home Plus Structures**

EHR tool	In the 2 study SNFs, an earlier version of the Connect-Home “ Transition Plan of Care Template ” was installed in the SNF EHR system. Before the pilot begins, the Transition Plan of Care template will be modified for Connect-Home Plus. The adapted template contains free text fields in 6 key care domains that SNF staff and home care RN, and dementia caregiver specialist (who makes post-discharge follow-up calls) use to record transition goals and deliver the two-step intervention.
Toolkit	The “ Connect-Home Plus Toolkit ,” a staff training workbook, based on the version of the workbook that was previously used in the parent study. It contains the Connect-Home Plus EHR template, 2-step intervention protocol, checklists and cue sheets, and intervention schedule.
Staff Training	
Site Leadership Training (1 hour). PI trains 1-2 SNF project leaders. Content: the Connect-Home Plus protocol and study procedures.
 
Staff Training (2 hours) In each SNF, the SNF staff were previously trained with the Connect-Home protocol. Thus, staff training with the Connect-Home Plus protocol will be two hours (as opposed to 4 hours in the parent study), with a special focus on services to care for persons with ADRD and their caregivers. The PI will train social workers, nurses, rehabilitation therapists. Training content: 1) Patient and caregiver key care needs (home safety and level of assistance, advance care planning, symptom management, medication reconciliation, function and activity, and coordination of follow-up medical care). 2) Protocols for using the two-step intervention to address patients’ key care needs and unique needs of persons living with dementia and their caregivers. 3) Using the EHR template to individualize patients’ Transition Plan of Care. 4) Advance care planning (identify surrogate, Health Care Power of Attorney, existing advance directives). 5) Integrating SNF-based and home-based care (e.g., clinical hand-offs from SNF to home care RNs, the dementia caregiver specialist, and follow-up medical providers). Teaching Strategy: Presentation, the Connect-Home Plus Toolkit and teach-back.
 
Focused Training for Home Care RNs (1.5 hours). The PI will provide additional training for home care RNs in up to 3 home care agencies that will participate in the pilot study (Table 2, below). Training content: The importance of home care follow-up within 24 hours of discharge, strategies for implementing the Transition Plans of Care, key care needs of persons living with ADRD and their caregivers and responding to medical needs. Teaching strategy: Presentation, the Connect-Home Plus Toolkit and teach-back.
 
Focused Training for Dementia Caregiver Specialist (2 hours). The PI will train an occupational therapist to serve in the role of dementia caregiver specialist. Training content: 1) the Connect-Home schedule of care, 2) the Transition Plan of Care, 3) key care needs of persons living with ADRD and their caregivers, 4) the post-discharge call back script, 5) procedures for communication with the SNF staff, and 6) procedures for maintaining a record of call backs using the Call-
 
New Staff Training (1-2 hours, as needed): The PI trains replacement staff to use the Connect-Home Plus protocol.


After new structural elements are in place, SNF staff will use Connect-Home Plus care processes to deliver the 2-step transitional care intervention. In **Step 1**, SNF nurses, rehabilitation therapists, and social workers will develop

a Transition Plan of Care and prepare the patient and caregiver to manage the patient's unique care needs related to ADRD and other functional and health care needs at home. In **Step 2**, a home care RN will visit the patient and caregiver at home within 24 hours of discharge; the nurse will work with them to activate the Transition Plan of Care at home. In addition, the Dementia Caregiver Specialist will call the caregiver at home to reinforce the discharge plan that was developed in the nursing home. The Dementia Caregiver Specialist will call within 72 hours of the patient's discharge to home and up to two more times, within one month of the discharge to home. See Table 5.

**Table 5. Connect-Home Plus transitional care processes**

Process	Patient/Caregiver Services and Supports	Day
Step 1. Transitional care in the SNF	
Set goals for home-based care (45 minutes)
 
Consulting with the patient/caregiver, SNF staff use the EHR template to describe goals in the patient's Transition Plan of Care, targeting key care needs and tailoring goals to the unique needs of persons with ADRD and their caregivers. The staff will identify concordance of observed signs and symptoms of impairment in the patient's thinking and memory (or other behavioral impairments) and the evidence of impairment from standardized assessments of cognitive impairment in the Minimum Data Set (e.g., BIMS score), other standardized measures of cognitive impairment staff use in routine care, and/or a diagnosis of dementia of any type in the medical record.
 
 
• Nurses create goals for treatments and responses to symptoms or other health changes
 
• Rehabilitation therapists create goals for mobility, transfers and self-care.
 
• Social worker creates goals for caregiver support, follow-up care & discharge
 
	2 - 17
	
Meet to plan the patient's transition to home-based care (30 minutes)
 
In dialogue with the patient/caregiver, the treating nurse, social worker and therapists will develop a plan for home-based care, targeting key care needs. The SNF staff members will discuss evidence of impairment in the patient's thinking and memory and/or the diagnosis of dementia, the caregiver's understanding of impairment in thinking or memory, and unique care needs and plans for coordinating the patient's transition to home. The staff will assist the patient and caregiver with planning for safety at home.
 
 
• Nurses focus on medications, advance care planning and symptom management.
 
• All staff help the patient and caregiver describe their needs for continuing care at home.
 
• Social worker reviews Transition Plan of Care, home care plans, and the dementia caregiver specialist call-backs.
 
	5 - 10
	
Prepare the patient and caregiver for home-based care (2.5 hours)
 
 
1. Teach skills and plans for home-based care, targeting key care needs. 
 
• Nurses teach symptom management (e.g., pain), clarify advance care planning preferences, and reconcile medication orders
 
• Rehabilitation Therapists teach skills for function and safety at home.
 
• Social worker schedules and explains appointments, home-based care & cost
 
 
 
2. Initiate hand-off to home-based care (over the last 1-2 days before discharge) 
 
• SNF staff send medical records and copies of any advance care planning documents to the patient's physician and the home care RN. Provide caregiver with the Connect-Home Plus Discharge Planner) and notify the dementia caregiver specialist of the day of discharge.
 
 
 
 
Nurses: 1) reconcile medications, 2) provide supplies and medications, and 3) re-teach the written Transition Plan of Care and medication list.
	6 - 20

Step 2. Transitional care in the patient's home	Implement the Transition Plan of Care at home (3 hours) Home care RN visits the patient and caregiver at home within 24 hours of discharge to: 
 
• reconcile medications on the discharge medication list and in the home,
 
• help family implement new care routines, addressing key care needs,
 
• conduct a brief home safety & falls prevention screen
 
 Dementia Caregiver Specialist calls the caregiver within 72 hours of discharge and two more times within one month of discharge (20 minutes / call) 
 
• Answer caregiver questions about implementing new routines of care at home
 
• Provide education about care of a person living with ADRD and the unique care needs of a care transition for a person with ADRD. Relay information
 
	21 (home care visit) & before day 51 (3 call backs)
---	---	--

